11. APPENDICES

STUDY SUMMARY

- TITLE** A PROSPECTIVE MULTI-CENTER RANDOMIZED STUDY ON TOTAL HIP REPLACEMENT WITH E1
- DESIGN** PROSPECTIVE, RANDOMIZED, MULTI-CENTER
- PURPOSE** Evaluate E1 wear, clinical outcomes and quality of life on patients who received THA with E1
- POPULATION** 160 hips
- DURATION** EXPECTED DURATION OF THE PATIENT RECRUITMENT IS 1 YEAR. LAST FOLLOW-UP IS AT 10-YEAR AND THE EXPECTED COMPELITION DATE FOR THE LAST ENROLLED DATE IS 11 YEARS AFTER THE FIRST ENROLLMENT.

1. INTRODUCTION

1.1. BACKGROUND

Total hip arthroplasty (THA) is one of the most successful surgical procedures in general. Yet, a few problems remain unsolved, and aseptic loosening is probably the most important of them. One of the main reasons for aseptic loosening in THA is the foreign body reaction caused by the wear particles. Since the late 1990s, the orthopedic industry has been developing highly crosslinked polyethylene (HXLPE) materials to capitalize on the increased wear resistance. In 2007, E1® Antioxidant Infused Technology was developed to reduce wear rate, maintain mechanical properties and prevent oxidative degradation. In late 2010, E1® Acetabular Liners was introduced and has been used widely in Japan.

Also alumina ceramic was introduced as a bearing surface in the 1971 as an alternative to the metal on-polyethylene couplings. Since then, alumina ceramic has been used in THA successfully for more than 35 years. BIOLOX®Delta is designed with improved fracture toughness, further reduces the risk of fracture and also extends the design flexibility of the material.

However, there are a few clinical data collected on wear and performance of E1® Liners available for Caucasian population and no data for Japanese today. There is no clinical data of BIOLOX®Delta femoral head articulating against E1® Liner. Therefore, it is needed to collect clinical data to support marketing and validate design of E1® Liners in terms of its safety and efficacy.

1.2. DEVICE DESIGN AND DESCRIPTION*

All patients will receive the vitamin E treated polyethylene "E1® Liners". Short-term femoral head penetration and long-term steady state wear of the polyethylene will be measured using software.

The investigational group, Ceramic-on-Polyethylene (CoP) total hip prosthesis, consists of BIOLOX® Delta ceramic modular femoral head articulating against E1® Liner. The ceramic femoral head is attached to a conventional femoral stem to complete the CoP total hip prosthesis device configuration.

The control group, Metal-on-Polyethylene (MoP) hip prosthesis, consists of the commercially available cobalt chrome (CoCr) femoral head articulating against E1® Liner. The metal femoral head is attached to a conventional femoral stem to complete the MoP total hip prosthesis device configuration.

- E1® Acetabular Liners: flat (MaxRom, MaxRom+) and hi-wall (Hi-Wall, Hi-wall+) style liner used for both the investigational (CoP) and control (MoP) cohorts.
 - 28, 32 and 36mm inner diameters are available and 40mm will be available in mid CY 2012.
- BIOLOX®Delta femoral heads: used for the investigational cohort. The BIOLOX® Delta ceramic femoral heads are manufactured from BIOLOX® delta, an alumina composite matrix.
 - 28, 32, 36 and 40mm head diameters will be available in mid CY 2012.
- Biomet cobalt-chrome femoral heads used for the control cohort
 - 28, 32, 36 and 40mm head diameters are available
- Any Biomet Femoral Component (Hip Stem) used for both the investigational and control cohorts
- RingLoc® PPS® or Ringloc+® Regenerex® Acetabular Shell System used for both the investigational and control cohorts.

1.3. RATIONALE FOR CURRENT STUDY

E1® Acetabular liners received approval in Japan in 2010. BIOLOX®Delta femoral heads has not been approved and estimated the approval in mid CY 2012. Currently there is no clinical data on E1® Acetabular liners implanted in Japanese population. There is a need to collect clinical data to investigate how this hip system performs in Japanese population.

1.4. PURPOSES

The primary objectives of this pilot clinical study include:

- Evaluate E1 Wear including early bedding-in process, clinical outcomes on patients who received THA with E1
- Compare E1 wear used with CoCr and Biolox Delta heads

2. STUDY DESIGN

2.1. OVERALL DESIGN

This study is a prospective, multi-center randomized controlled study and will be conducted in Japan at a maximum of 5 sites.

The study will consist of two phases, over a period of 11 years. Phase 1 will collect data on penetration rate recognized as “early bedding-in” and patients will be followed at immediate post-op, 6 months and 1

year, 2 years, 3 years. Phase 2 will collect data on penetration rate recognized as “steady-state wear” after 5 years, 7years and 10 years post-op.

2.2. NUMBER OF SITES AND SUBJECTS/PROCEDURES

Total of 160 hips will be enrolled in the study.

2.3. PRIMARY AND SECONDARY ENDPOINTS

PHASE 1: Immediate post-op to 3 years	
Primary endpoints	Early bedding in
Secondary endpoints	At all follow-up visits: Survivorship up to 3 years JOA Radiographic Assessment Complications including revisions
PHASE 2: 5 to 10 years	
Primary endpoints	Steady-state wear
Secondary endpoints	At all follow-up visits: Survivorship up to 10 years JOA Radiographic Assessment Complications including revisions

2.4. ASSESSMENT PROCEDURE

2.4.1. ASSESSMENT PARAMETERS AND METHODS

Medical History and Demographic Data

Demographic information will be collected, a detailed medical history will be obtained and a physical examination will be performed (including height, weight).

Clinical Assessments

An operative record will be completed to record details of each operative procedure and of the used implants.

Data to determine the clinical and functional performance of the device will be collected. Pre-operative and post-operative analysis will be compared using recognized and validated systems (JOA Score).

Radiographic Assessments (including Radiographic Assessment protocol)

A radiographic assessments including polyethylene wear analysis and cup inclination angle will be completed at each follow-up period.

The X-rays must be taken according to the Martell technique*, which requires an A/P pelvis view centered over the pubis. See attachment for radiographic technique.

For the polyethylene wear analysis, all Radiographic images will be determined and the penetration rate will be measured by Hip Analysis Suite (software program, [name] at Chicago University).

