2.5. Randomization

Patients will be randomized to receive Delta Ceramic Head (investigational group), or CoCr Head (control group). Patients have an equal opportunity of being assigned to the investigational group or control group. Specifically:

In case of unilateral patients, the affected side of hip will be randomized to one of two groups. In case of bilateral patients, both sides of hip will be randomized to the same device (Delta Ceramic or CoCr).

The randomization will occur via a random number generator (manual or computer). Block randomization will be used. Blocks of K patients will be created where K = 4.

The possible sequences are AABB, BBAA, ABAB and BABA. Two sets of randomization blocks will be followed by unilateral and bilateral patients respectively.

For unilateral patients, A or B represents the device assigned to affected side of the hip. For bilateral patients, A or B represents the device assigned to both affected sides of the hip.

The doctor or other health care professional does not choose the participants for each group. For Patients satisfying inclusion criteria, randomization will occur by retrieving the next randomly generated group assignment.

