5. STATISTICAL ANALYSIS PLAN

5.1. Sample Size Calculation

The study population is calculated based on the primary endpoint of Poly wear at 10 year postop. A total of 160 hips will be recruited the study and randomly assigned to either CoCr or Ceramic head group. Each site is required to use the same stem and cup for both CoCr and Ceramic groups.

Significance Level = 5 % (95% confidence)

$d = 0.5$ mm Clinically significant difference in wear.

$\xi = 0.07$ Estimate standard deviation of wear.

$N = 63$

Take into consideration of Lost-to-Follow-up Rate = 20% for 10 year

Final N = 80 hips per group

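### The only stated JOA comparison is before versus after surgery, which gives no estimate of the difference between the randomised heads; add a between-arm analysis adjusted for pre-operative JOA

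*Combined protocol and SAP*

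**What the plan says.** Section 2.3 lists JOA among the Phase 1 secondary endpoints at all follow-up visits ("Survivorship up to 3 years JOA Radiographic Assessment Complications including revisions"), and the Phase 2 list names it again. The schedule in 2.4.2 has JOA pre-operatively and at 6 months and 1, 2, 3, 5, 7 and 10 years.

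How JOA is to be compared is stated once, under Clinical Assessments in 2.4.1: "Pre-operative and post-operative analysis will be compared using recognized and validated systems (JOA Score"). The sentence does not say whether this is done within each arm or with the arms pooled.

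The trial is randomised by head type. Section 2.5 says: "Patients will be randomized to receive Delta Ceramic Head (investigational group), or CoCr Head (control group"). Unilateral and bilateral patients follow separate sets of blocks. Both hips of a bilateral patient get the same head: "In case of bilateral patients, both sides of hip will be randomized to the same device (Delta Ceramic or CoCr").

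Section 1.4 gives two aims: "Evaluate E1 Wear including early bedding-in process, clinical outcomes on patients who received THA with E1" and "Compare E1 wear used with CoCr and Biolox Delta heads". Only the second contrasts the heads, and it concerns wear.

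Section 5 sizes the trial on wear. Its Data Analyses part gives the timing of interim and final analyses. It names no test, model, covariate or arm contrast for any endpoint.

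**The concern.** Surgery separates the pre-operative from the post-operative score, and both arms have surgery. A before-after comparison therefore shows how patients change after hip replacement. Within arms or pooled, it leaves the effect of the head unestimated.

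This matters because the design can answer that question. Section 1.2 labels the ceramic head investigational and the CoCr head control, and section 1.1 says there are no clinical data on the Delta head against the E1 liner. JOA will be measured at seven follow-up visits in two randomised groups. Without a stated contrast, the analyst must choose among post-operative scores, change scores and baseline-adjusted scores after data have been seen. Interim analyses are planned at 1, 2, 3, 5 and 7 years before the final one. As shown below, the three choices differ in precision.

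**Working it through.** **Plan's own figure.** None exists for JOA. The wear calculation gives N = 63 per group before loss to follow-up. That number serves below only as an illustrative count of evaluable hips.

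**Inputs from the documents.** Allocation is 1:1 (2.5: "Patients have an equal opportunity of being assigned to the investigational group or control group"). The significance level comes from 5.1 ("Significance Level = 5 % (95% confidence"), taken here as two-sided because the plan does not say.

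**Assumptions, because the documents give no JOA figures.**
- Pre-post correlation r of 0.2, 0.3, 0.5 or 0.7, with one common r across visits.
- The same standard deviation σ in both arms and, for the change score only, the same σ before and after surgery.
- For the power figures, a true arm difference of 0.5σ and 63 hips per group treated as independent.

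**Variance of the arm difference with n hips per arm.**
- Post-operative score only: 2σ²/n, factor 1.
- Change score: factor 2(1 − r).
- Adjusted for pre-operative score: factor 1 − r².

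For r = 0.5: change 2 × 0.5 = 1.00; adjusted 1 − 0.25 = 0.75. Since 2(1 − r) − (1 − r²) = (1 − r)² ≥ 0 and 1 − r² ≤ 1, the adjusted analysis is never less precise than either alternative, apart from a negligible loss of degrees of freedom.

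**Power, normal approximation.** Power = Φ(0.5 × √(63/2) / √factor − 1.96). Post-only: 0.5 × 5.612 = 2.806; 2.806 − 1.96 = 0.846; power 80.1%. Adjusted at r = 0.5: 2.806/√0.75 = 3.240; 3.240 − 1.96 = 1.280; power 90.0%.

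| Assumed r | Change factor | Adjusted factor | Equivalent hips, 1/(1 − r²) | Power, post-only | Power, change | Power, adjusted |
|---|---|---|---|---|---|---|
| 0.2 | 1.60 | 0.96 | 1.04 | 80.1% | 60.2% | 81.7% |
| 0.3 | 1.40 | 0.91 | 1.10 | 80.1% | 66.0% | 83.7% |
| 0.5 | 1.00 | 0.75 | 1.33 | 80.1% | 80.1% | 90.0% |
| 0.7 | 0.60 | 0.51 | 1.96 | 80.1% | 95.2% | 97.6% |

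Under these assumptions adjustment adds between 1.6 and 17.5 percentage points of power over the post-operative score alone. A change-score contrast loses power when r is below 0.5. The plan does not propose that contrast; the column shows why the model should be named in advance.

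**The case against.** **The sentence is not an analysis choice.** A reader might infer that the plan puts a before-after comparison in place of an arm comparison. The documents do not support that. The sentence sits in the assessment section, names the instrument and says when it is used. It excludes nothing, and the analysis section is silent on method for every endpoint, wear included. This stands: the fault is an omission, and part of a wider one.

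**Before-after JOA fits a stated aim.** Section 1.4 asks for a head comparison on wear only; clinical outcomes are to be evaluated in E1 patients generally. Section 1.3 adds that data in Japanese patients are lacking. This also stands, so the before-after summary should be kept. It does not remove the gap, because the protocol randomises the heads, makes JOA a secondary endpoint and gives no way to compare JOA between them.

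**The baseline is not wasted.** A before-after comparison does use pre-operative JOA, though not as a covariate. Nor does the plan propose to judge the heads by which arm improves significantly; a reader could fear that misuse, but no text invites it.

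**The size is hypothetical.** Correct. A saving of a third in hips would need r = 0.5. At r = 0.3 it is about 10% and at r = 0.2 about 4%. One r from 6 months to 10 years is also doubtful.

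**Conclusion.** The point holds as an omission on a secondary endpoint. The stated before-after JOA comparison is legitimate description but gives no estimate of the difference between randomised heads, and no other JOA analysis is specified. That conclusion rests on the text alone and needs no assumed number.

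The gain in precision from adjustment does depend on assumptions. For r from 0.2 to 0.7 the variance of the arm difference falls to between 0.96 and 0.51 of the post-only value, so the benefit may be slight or large. The power figures also assume a 0.5σ difference and independent hips; correlated scores from bilateral patients on the same head would generally lower them. The primary wear endpoint is unaffected.

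**What to change.** In sections 2.4.1 and 5:

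- Keep the change from before to after surgery, labelled descriptive.
- Add a comparison of JOA between the ceramic and CoCr arms at each follow-up visit, using a linear (mixed) model with pre-operative JOA, unilateral/bilateral stratum and site as covariates. The stratum belongs there because the two types of patient are randomised from separate blocks. Site belongs there because 5.1 fixes stem and cup within each site.
- Treat patient as the cluster, since both hips of a bilateral patient receive the same head. If all visits enter one model, allow for repeated measurements as well.
- Report the adjusted mean difference with its 95% confidence interval.

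This costs wording and analysis time only. Pre-operative JOA is already scheduled, and no visit, patient or measurement is added.

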2.4.2. ASSESSMENT TIMELINES/SCHEDULE

Example of Tabulated Assessment Schedule

	PRE-OP	SURGERY	PHASE 1						PHASE 2		
			IMMEDIATE POST-OP	6 WK	6 MO	1 YR	2 YR	3 YR	5 YR	7 YR	10 YR
Informed Consent	X										
Demographic and Historical Record	X										
Operative Record		X									
Radiographic Assessment			X	(X*)	X	X	X	X	X	X	X
JOA	X				X	X	X	X	X	X	X
Complications including Revisions			ANYTIME								

* Baseline for bedding in and total penetration rate

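### The sections disagree on whether the 6-week baseline film is required, and section 5.1's 0.5 mm and SD 0.07 do not give 63 hips per group or refer to a defined Phase 2 endpoint

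*Combined protocol and SAP*

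**What the plan says.** **Baseline film.** In the section 2.4.2 schedule the asterisk sits only on the 6-week radiograph, and the footnote reads "Baseline for bedding in and total penetration rate". Every other scheduled film carries a plain cross; the 6-week cross is in brackets, with no explanation in the available text. In section 2.1, "patients will be followed at immediate post-op, 6 months and 1" year, then 2 and 3 years, with no week 6. Section 2.3 heads the first phase "PHASE 1: Immediate post-op to 3 years" and makes early bedding-in its primary endpoint. On the other side, section 2.4.3 gives week 6 a window of 4-8 weeks, and section 2.4.1 says: "A radiographic assessments including polyethylene wear analysis and cup inclination angle will be completed at each follow-up period".

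**Phase 2 endpoint and sample size.** Section 2.3 names "Steady-state wear" as the Phase 2 primary endpoint, without unit, visit or formula. Section 2.1 says "Phase 2 will collect data on penetration rate recognized as" steady-state wear "after 5 years, 7years and 10 years post-op". Section 5.1 (Sample Size Calculation) bases N on polyethylene wear at 10 years. It gives a significance level of 5%, a difference of 0.5 mm, an SD of 0.07 with no unit, N = 63, 20% loss over 10 years and a final 80 hips per group. It states no power.

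**The concern.** Bedding-in is penetration measured from a starting film, so the choice of film is part of the endpoint's definition. A site that works from section 2.1, or takes the brackets to mean that the film may be skipped, would have no stated baseline for its hips. The immediate post-op film is the obvious substitute. Using it would count penetration that occurs before week 6, and so measure a different quantity from that measured in hips with the 6-week film.

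For Phase 2, the sample size is the only place where the plan attaches numbers to a wear comparison. If those numbers do not produce the stated N, and the quantity sized is not clearly the endpoint named in section 2.3, a reader cannot tell what difference the trial can detect. There is also a question of interpretation. If 10-year wear means total penetration from week 6, it includes bedding-in after week 6, and a difference between arms in bedding-in could be read as a difference in long-term wear.

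**Working it through.** **1. The stated N.** Inputs from section 5.1: difference d = 0.5 mm, SD 0.07, 5% level (taken as two-sided), equal groups. Power is not stated, so 80% and 90% are assumed. Normal approximation: n per group = 2(z_alpha + z_beta)²(SD/d)².

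- As written, 80% power: 2 × 7.849 × (0.07/0.5)² = 0.31.
- As written, 90% power: 2 × 10.507 × (0.07/0.5)² = 0.41.
- With 0.5 read as a standardised difference, 80% power: 2 × 7.849/0.5² = 62.8, rounded up to 63 (64 with the t distribution). On the SD's scale this is 0.5 × 0.07 = 0.035.
- Allowing for loss: 63/0.8 = 78.75, so 79 against the stated 80; 64/0.8 = 80. This step is not a problem.

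A further reading spreads 0.5 mm over 10 years (0.05 mm/year) and assumes that 0.07 is in mm/year. It gives 31 hips per group at 80% power and 42 at 90%; 63 would then correspond to 98% power. So 63 does not follow from 0.5 mm and 0.07 as written. At conventional power it follows from 0.5 SD.

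**2. Does a mixed baseline change the interval?** Using the section 2.4.3 windows and 4.348 weeks per month:

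- 3-year visit, 6-week film only: 135.5 to 165.6 weeks, a 1.22-fold spread. With some hips measured from the immediate post-op film: 135.5 to 169.6 weeks, 1.25-fold.
- 6-month visit: 13.7 to 26.4 weeks (1.92-fold), against 13.7 to 30.4 (2.22-fold).

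Interval length changes little, especially at 3 years. What changes is whether penetration before week 6 is counted. The documents give no figure for that, nor for how often the film would be missed, so no bias can be computed.

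**3. Bedding-in carried into 10-year wear.** Assume that 10-year wear is total penetration from week 6, that steady-state wear is equal in the two arms, that hips are independent and that there are 63 per group. SE = SD × √(2/63). The chance of a significant result from an arm difference in bedding-in alone is as follows (offsets and total SDs assumed):

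| Total SD (mm) | 0.01 mm | 0.02 mm | 0.035 mm | 0.05 mm |
|---|---|---|---|---|
| 0.07 | 12.6% | 36.1% | 80.1% | 98.0% |
| 0.099 | 8.8% | 20.5% | 51.0% | 80.9% |
| 0.140 | 6.9% | 12.6% | 28.9% | 51.8% |
| 0.504 | 5.1% | 5.6% | 6.8% | 8.6% |

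The first row takes section 5.1's 0.07 as the SD in mm of total penetration. The others take 0.07 mm as the error SD of a single film, with a true between-hip SD of 0, 0.01 or 0.05 mm/year over 9.885 years (10 years less 6 weeks): total SD = √(9.885² × t² + 2 × 0.07²), where t is the between-hip SD. If 0.07 is in mm/year, the total SD is 0.07 × 9.885 = 0.692 mm and the chances are 5-7%.

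**4. Precision of a late slope.** A constant early offset contributes nothing to a slope over years 5, 7 and 10. The sum of squares of those times about their mean is 12.67. With film error alone, slope variance is 1/12.67 = 0.0789 per unit of error variance, against 2/9.885² = 0.0205 for the total rate: a ratio of 3.86. With film-error SD 0.07 mm and between-hip SD 0.01, 0.02 or 0.05 mm/year (assumed), the ratio (t² + 0.07²/12.67)/(t² + 2 × 0.07²/9.885²) is 2.43, 1.57 or 1.11.

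**The case against.** On the baseline, the two operative tables both contain week 6, and only the narrative in section 2.1 leaves it out. The brackets may do no more than set off the footnoted cell. Section 2.4.1 also says "See attachment for radiographic technique", and neither that attachment nor the case report forms are in the available text, so a rule for a missing film may exist there. All of this stands. A reader might infer that the 6-week film is optional; the documents do not say so. They show only that the sections do not agree.

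On Phase 2, steady-state wear has no formula. A rate calculated at each late visit from the stated baseline fits section 2.1 as well as a rate fitted across years 5, 7 and 10. Section 5.1 calls its quantity the primary endpoint, and 10 years is a Phase 2 visit, so loose naming is possible. A reader might infer that the trial was sized on a different endpoint from the one in section 2.3. The documents do not show this, because that endpoint is not defined closely enough to compare.

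The first row of the table also invites the conclusion that a small bedding-in difference would very likely produce a misleading long-term result. That row rests on one reading of an SD without a unit; other readings bring the chance close to 5%. Moreover, a difference in total penetration caused by bedding-in is a real difference, and only its label as long-term wear would be wrong.

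Finally, a late slope is not clearly the better primary measure, since it removes the early offset at a cost in precision. None of these objections restores the arithmetic in section 5.1.

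**Conclusion.** Both parts hold, at different strengths.

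The sample-size statement is wrong as written: 0.5 mm with an SD of 0.07 leads to less than one hip per group, not 63. The stated N matches 0.5 SD at 80% power, a much smaller difference (0.035 on the SD's scale) than the 0.5 mm described as clinically significant. This rests on a two-sided 5% test and the normal approximation. It does not show that 80 hips per group is too few. That cannot be judged until the endpoint, its units and its SD are stated.

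The baseline film is a conflict between sections that bears on a primary endpoint and is cheap to remove. Its effect on the results cannot be quantified from the documents.

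The possible carry-over of bedding-in into 10-year wear is a reason to define steady-state wear clearly, not a demonstrated error. Over offsets of 0.01 to 0.05 mm, the chance of a significant result from bedding-in alone is 13-98% at a total SD of 0.07 mm, 9-81% at about 0.10, 7-52% at 0.14 and 5-9% at about 0.50. These SDs are assumed and hips are treated as independent. Section 2.5 gives both hips of a bilateral patient the same device, so independence will not hold for those patients.

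**What to change.** **Baseline.** Reconcile sections 2.1, 2.4.2 and 2.4.3 so that the 6-week film named in the footnote is the baseline for every hip in both arms: list week 6 in section 2.1 and remove or explain the brackets. Use the immediate post-op film only in a sensitivity analysis. The cost is small. No film is added to the section 2.4.2 schedule, but a site that has been skipping week 6 would have to take it.

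**Phase 2 endpoint and section 5.1.** Define steady-state wear by unit, visits, baseline and formula, in a way that does not mix it with bedding-in. Then restate the difference, SD, units, power and resulting N in section 5.1 for that endpoint. Keep 80 hips per group, and say that hips from bilateral patients are not independent. This is a change of wording and calculation; its downside is that the restated figures may be less favourable than those now given.

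**Optional.** A slope over years 5, 7 and 10 can be reported alongside the total rate. It should not be a required replacement, because its variance is about 1.1 to 3.9 times as large under the assumptions above.

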2.4.3. ALLOWED WINDOW OF EACH SCHEDULE

PHASE	Evaluation Schedule		
	Interval	Follow-Up Window	Months Post-Op Range
PHASE 1	Immediate Post-Op	± 2 weeks	Immediate post-op < 2 weeks
	6 weeks	± 2 weeks	4-8 weeks
	6 month follow-up	± 1 month	5-7 months
	1 year follow-up	± 2 months	10-14 months
	2 year follow-up	± 3 months	19-27 months
	3 year follow-up	± 3 months	33-39 months
PHASE 2	5 year follow-up	± 3 months	57-63 months
	7 year follow-up	± 3 months	81-87 months
	10 year follow-up	± 3 months	117 – 123 months

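### The schedule zeroes early bedding-in at the 6 week film, although the bedding-in phase starts at immediate post-op, so the Phase 1 primary endpoint, read literally, leaves out the first weeks

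*Combined protocol and SAP*

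**What the plan says.** Section 2.3 heads the first part of the endpoint table "PHASE 1: Immediate post-op to 3 years" and names "Early bedding in" as its primary endpoint, with no formula and no start or end film. Section 2.1 ties Phase 1 to the bedding-in penetration rate and says that "patients will be followed at immediate post-op, 6 months and 1" year, then at 2 and 3 years. It lists no 6 week visit.

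In the radiograph row of the 2.4.2 schedule, the immediate post-op cell holds a plain X. The 6 week cell holds a bracketed and starred X, the only one in the row, and the footnote explains the star as "Baseline for bedding in and total penetration rate". The brackets are not explained. Section 2.4.3 gives the 6 week film a window of 4 to 8 weeks and the immediate film the range "Immediate post-op < 2 weeks".

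The objectives in 1.4 include "Evaluate E1 Wear including early bedding-in process" and "Compare E1 wear used with CoCr and Biolox Delta heads".

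**The concern.** Penetration is a change between two films. If the first is the 6 week film, whatever happened between surgery and that film falls out of the result. For a steady-state slope between late films this does not matter. For bedding-in it does, because the endpoint is meant to describe the early process.

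The 6 week film is also taken after randomisation and implantation. If the ceramic and CoCr heads differ in the first weeks, that difference sits inside the baseline and is removed from the comparison. The objective of describing bedding-in and the objective of comparing heads are therefore both affected, on the Phase 1 primary endpoint. A film that could cover most of the gap is already in the schedule, but the plan gives it no role as a wear baseline.

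**Working it through.** **Reading the schedule.** The radiograph row has nine marks for nine post-operative columns (immediate, 6 weeks, 6 months, then 1, 2, 3, 5, 7 and 10 years). The starred mark is the second, so it belongs to the 6 week column. The window agrees with its stated tolerance: 6 − 2 = 4 and 6 + 2 = 8 weeks.

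**What each baseline measures.** Let P(t) be true penetration at time t after surgery, and let E be the film that ends the bedding-in period.

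- From the 6 week film: P(E) − P(6 wk).
- From the immediate film at time t0, with t0 under 2 weeks: P(E) − P(t0).
- Difference between the two: P(6 wk) − P(t0), the immediate-to-6-week increment.

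The same holds for the difference between arms. The 6-week-based comparison omits the arm difference in P(6 wk), and the immediate film would restore all of it except the part before t0. This needs no assumption about the shape of P.

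**Size, by assumption only.** The plan has no figure to reproduce here and no penetration-by-time data. Assume P(t) is proportional to 1 − exp(−t/T), with T = 0.25, 0.5 or 1 year, and convert weeks to years: 2, 4, 6 and 8 weeks = 0.038, 0.077, 0.115 and 0.153. Worked case: 1 − exp(−0.115/0.25) = 1 − exp(−0.46) = 0.37.

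| T | complete at 6 wk | range over 4 to 8 wk | complete at 2 wk | recoverable, in points |
|---|---|---|---|---|
| 3 months | 37% | 26% to 46% | 14% | 23 to 37 |
| 6 months | 21% | 14% to 26% | 7% | 13 to 21 |
| 12 months | 11% | 7% to 14% | 4% | 7 to 11 |

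The last column assumes a 6 week film taken at 6 weeks. Its lower end is the 6 week share minus the 2 week share, from unrounded values, for an immediate film at the limit of its window. Its upper end is for a film on the day of surgery. If the head difference is proportional to penetration throughout, it shrinks by the share in the second column.

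Other assumed shapes widen the range. The share complete at 6 weeks is 6/156 = 4% if bedding-in is linear over 3 years, 6/52 = 12% if linear over 12 months and 6/26 = 23% if linear over 6 months. For exponential courses it is 1 − 0.5^(6/13) = 27% with a 13 week half-life and 1 − 0.5^(6/6) = 50% with a 6 week half-life.

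I give no loss of power. The sample size in 5.1 was set for wear at 10 years, and the documents give no standard deviation for bedding-in.

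**The case against.** The strongest reply is that this is a design choice applied alike to both randomised arms, in a study that calls itself a pilot. A 6 week baseline could be deliberate, since films soon after surgery may be noisier because of positioning or loading. The radiographic technique attachment is not available here and might address this. That stands as a reason to keep the 6 week baseline. It does not supply a reason in the plan's text, and it does not conflict with reporting a second value.

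Several stronger readings are tempting, and the documents do not support them.

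- A reader might infer that the immediate film goes unused. Section 2.4.1 calls for wear analysis at each follow-up period and says that all images are to be assessed, and 2.3 lists radiographic assessment as a secondary endpoint at all visits. The film is probably read already. What is missing is a stated wear baseline that uses it.
- A reader might infer that 2.3 defines bedding-in as starting at surgery, so that the footnote is simply wrong. The heading in 2.3 sets the period for all Phase 1 endpoints, including survivorship and JOA, and is not a formula. The endpoint has none. The exclusion rests on the footnote taken literally, and the firm finding is that 2.1, 2.3 and the footnote do not agree.
- A reader might infer that a hip filmed at week 8 loses twice as much bedding-in as one filmed at week 4. That is true of elapsed time only. On the exponential curves above the ratio is about 1.7 to 1.9.
- A reader might infer that the window adds noise to the endpoint. This is not shown. Sections 2.1 and 2.4.1 speak of a penetration rate, and if time since baseline is the denominator, part of the variation in film date is absorbed.

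**Conclusion.** The point holds in a limited form. The only operational baseline rule places zero for bedding-in at 4 to 8 weeks, while the design and endpoint sections start the phase at immediate post-op, and nothing in the documents reconciles them. Followed literally, the rule leaves out penetration before the 6 week film and any head difference in that interval. This would be so even if every 6 week film were taken.

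The size cannot be found from the documents. The exponential illustration puts 11% to 37% of bedding-in before a film taken at 6 weeks, and the other assumed shapes extend this to between 4% and 50%. The immediate film would not recover all of it, because it too may be up to 2 weeks late. No bias in favour of either head is shown. What is at risk is that the trial cannot describe or compare the earliest part of the process it set out to measure. The change is worth making because the film is already scheduled.

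**What to change.** Reconcile 2.1, 2.3 and the 2.4.2 footnote, so that the start of bedding-in is stated once and the two uses of the baseline are separated:

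1. Keep the 6 week film as the baseline for total penetration rate.
2. For the Phase 1 primary endpoint, keep the 6-week-based value and report alongside it, by arm, the bedding-in penetration from the immediate post-op film and the immediate-to-6-week increment.
3. Use actual film dates throughout, so that the 4 to 8 week and under-2-week windows are visible in the analysis.

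The cost is footnote wording and one further reported contrast by arm. No visit, film or patient is added, and the software reading of the immediate film is probably planned already under 2.4.1. The downside is that early films may be noisier. Reporting both values shows whether they are, and leaves the 6-week-based result intact.
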